8.3.5. Regulatory Reporting Requirements for SAEs

Prompt notification by the investigator to the sponsor of a SAE is essential so that legal obligations and ethical responsibilities towards the safety of participants and the safety of a study intervention under clinical investigation are met.

The sponsor has a legal responsibility to notify both the local regulatory authority and other regulatory agencies about the safety of a study intervention under clinical investigation. The sponsor will comply with country-specific regulatory requirements relating to safety reporting to the regulatory authority, Institutional Review Boards (IRB)/Independent Ethics Committees (IEC), and investigators.

Investigator safety reports must be prepared for suspected unexpected serious adverse reactions (SUSAR) according to local regulatory requirements and sponsor policy and forwarded to investigators as necessary.

An investigator who receives an investigator safety report describing a SAE or other specific safety information e.g., summary or listing of SAEs) from the sponsor will review and then file it along with the Investigator's Brochure and will notify the IRB/IEC, if appropriate according to local requirements.

8.3.6. Pregnancy

8.3.6.1. Pregnancy testing

Women of childbearing potential must have a negative pregnancy test at Screening, and at Baseline (Day 1). Pregnancy testing will also be conducted as per the SoA (Section 1.3) and at any time during the trial when pregnancy is suspected.

Additionally, the Medical Monitor may request that a urine pregnancy test be performed in the event of a treatment interruption greater than 7 days.

If pregnancy is confirmed, a discussion with the pregnant study participant assessing the benefit/risk assessment of continuing in the study will be undertaken. If, after this discussion, the participant would like to continue in the study, this will be allowed, provided the pregnant participant signs the pregnancy specific ICF addendum. See [Appendix 6](#) for details. The above is applicable to participants randomised to CAB+RPV and not to participants on BIK.

Pregnant participants who remain in the study do not need pregnancy testing during the study, for the duration of their pregnancy.

8.3.6.2. Rationale for Continued Use in Pregnancy

Additional data regarding the use of CAB + RPV LA during pregnancy and management of pregnant participants remaining in the study are found in [Appendix 6](#).

The use of CAB + RPV LA during pregnancy may offer unique benefits. It is well documented that treatment adherence challenges to oral therapy exists both in the peri-partum and post-partum periods with LA dosing offering a unique opportunity to overcome such adherence challenges. LA therapy may also help with nausea (50% mild

to moderate) or hyperemesis (2%) that is frequently seen, especially during the first trimester of gestation.

Participants on LA dosing who become pregnant will have exposures throughout pregnancy due to the long half-life and PK tail of CAB/RPV. Prior to this protocol amendment, pregnant participants would have been withdrawn from the study, and initiated on an alternative oral ART regimen. Alternative regimens consist of either 2 or 3 antiretrovirals to protect the life of the mother and for the prevention of MTCT. This regimen, combined with the long half-life and PK tail of CAB/RPV would potentially expose the fetus to additional ARVs during gestation (in some cases upwards of 5 antiretrovirals).

Given the risk/benefit ratio for CAB + RPV LA dosing in WOCBP coupled with concerns of increasing fetal exposure to several additional antiretrovirals upon participant withdrawal, this amendment to the protocol will allow pregnant participants to remain in the study after a pregnancy specific ICF addendum is signed by the participant

8.3.6.3. Time Period for Collecting Pregnancy Information

Pregnancy information will be collected from Day 1 until the last follow-up assessment. This includes the entirety of the LTFU Phase.

Pregnant study participants who consent to remain in the study during pregnancy will continue to have all clinical assessments (with the exception of pregnancy tests) performed as per the Schedule of Activities (Section 1.3), including the collection of additional PK samples for CAB and RPV. See [Appendix 6](#) for details.

Pregnant participants who have received at least one dose of CAB LA or RPV LA and do not continue in the study during pregnancy will enter the Long-Term Follow-Up Phase of the study and will be monitored for 52 weeks after the last dose of CAB + RPV LA. Moreover, an alternative oral HAART will be initiated, at the discretion of the PI and in discussion with the Medical Monitor. If a participant becomes pregnant within 52 weeks of the last dose of study drug, the participant should notify the study site.

8.3.6.4. Action to be Taken if Pregnancy Occurs

Any pregnancy that occurs during study participation must be reported using a clinical trial pregnancy form. The investigator should inform GSK within 24 hours of learning of the pregnancy and should follow the procedures outlined in [Appendix 6](#).

Pregnant participants who elect to continue in the study and receive CAB + RPV LA must sign a pregnant specific ICF addendum. Cabotegravir and rilpivirine are detected in systemic circulation for up to 12 months or longer after discontinuing injections of CAB + RPV LA; therefore, consideration should be given to the potential for fetal exposure during pregnancy and should be discussed between the study participant and the study PI.

Participants who become pregnant during the study and elect to continue in the study and receive CAB + RPV LA will have additional PK samples collected to monitor CAB LA and RPV LA exposure throughout the pregnancy (see [Appendix 6](#)) and at the time of delivery.

Any SAE occurring in association with a pregnancy brought to the investigator's attention after the participant has completed the study and considered by the investigator as possibly related to the study treatment, must be promptly reported to ViiV/GSK.

GSK's central safety department will also forward this information to the Antiretroviral Pregnancy Registry. The international registry is jointly sponsored by manufacturers or licensees of ARV products. Additional information and a list of participating manufacturers/licensees are available from <http://apregistry.com/index.htm>.

8.3.7. Disease-Related Events and/or Disease-Related Outcomes Not Qualifying as SAEs

Disease related events (DREs) or outcomes listed in the CDC Classification System for HIV-1 Infections (Section [10.3](#)) can be serious/life threatening and will be recorded on the HIV-Associated Conditions eCRF page if they occur. These individual events or outcomes, as well as any sign, symptom, diagnosis, illness, and/or clinical laboratory abnormality that can be linked to any of these events or outcomes are not reported to GSK as AEs and SAEs even though such event or outcome may meet the definition of an AE or SAE. If any of the conditions below is met, then record the event on either the AE or SAE page (according to severity) in addition to the HIV Associated Conditions eCRF page. If it is categorized as an SAE, report promptly (i.e., expedited reporting), see Section [8.3.4](#), to GSK

- The investigator determines that the event or outcome qualifies as an SAE under part 'other situations' of the SAE definition (see Section [10.2.2](#)), or
- The event is, in the investigator's opinion, of greater intensity, frequency, or duration than expected for the individual participant, or
- The investigator considers that there is a reasonable possibility that the event was related to treatment with the investigational product, or
- Death occurring for any reason during a study, including death due to a disease-related event, will always be reported promptly.
- Lymphomas and invasive cervical carcinomas are excluded from this exemption; they must be reported as SAEs even if they are considered to be HIV-related.

8.3.8. Medical Device Deficiencies

The vial adaptor, syringe, and needles used in the study are classed as medical devices by the FDA. To fulfil regulatory reporting obligations worldwide, the investigator is responsible for the detecting and documentation of events meeting the definitions of device deficiency that occur during the study with such devices.

The definition of a medical device deficiency can be found in Section [10.9](#).

Instructions for medical device use are provided in the Study Reference Manual.

All device deficiencies, (including malfunction, use error and inadequate labelling) shall be documented, and reported by the investigator to the manufacturer of the device (if known)

NOTE: The medical devices supplied for the trial will not be supplied or manufactured by GSK/ViiV, reports of medical device deficiencies should be reported to the device manufacturer (if known) through the manufacturers' complaints process.

8.3.8.1. Time Period for Detecting Medical Device Deficiencies

- Medical device deficiencies that result in an incident will be detected, documented, and reported during all periods of the study in which the medical device is used.
- If the investigator learns of any device deficiency at any time after a participant has been discharged from the study, and such device deficiency is considered reasonably related to a medical device provided for the study, the investigator will notify the manufacturer of the device (if known) within 24 hours.

8.3.8.2. Follow-up of Medical Device Deficiencies

- Follow-up applies to all participants including those participants who discontinue study intervention or the study and associated persons.
- The investigator is responsible for ensuring that follow-up includes any supplemental investigations as indicated to elucidate the nature and/or causality of the deficiency.

8.3.8.3. Prompt Reporting of Medical Device Deficiencies to Manufacturer

- Device deficiencies will be reported to the manufacturer of the device (if known) within 24 hours after the investigator determines that the event meets the protocol definition of a device deficiency.

8.3.8.4. Regulatory Reporting Requirements for Medical Device Deficiencies

The investigator will promptly report all deficiencies occurring with any medical device used for CAB+RPV in the study, to the manufacturer of the device (if known). In order for the manufacturer to fulfil the legal responsibility to notify appropriate regulatory

authorities and other entities about certain safety information relating to medical devices being used in clinical studies.

8.3.9. Cardiovascular and Death Events

Investigators will be required to fill out the specific CV event page of the eCRF for the following AEs and SAEs:

- Myocardial infarction/unstable angina
- Congestive heart failure
- Arrhythmias
- Valvulopathy
- Pulmonary hypertension
- Cerebrovascular events/stroke and transient ischemic attack
- Peripheral arterial thromboembolism
- Deep venous thrombosis/pulmonary embolism
- Revascularisation

This information should be recorded in the specific cardiovascular eCRF within one week of when the AE/SAE(s) are first reported. The CV CRFs are presented as queries in response to reporting of certain CV MedDRA terms.

For any cardiovascular events detailed above, whether or not they are considered SAEs, and all deaths, specific Cardiovascular (CV) and Death Sections of the eCRF will be required to be completed. These sections include questions regarding cardiovascular (including sudden cardiac death) and non-cardiovascular death.

The CV CRFs are presented as queries in response to reporting of certain CV MedDRA terms. The CV information should be recorded in the specific cardiovascular section of the eCRF within one week of receipt of a CV Event data query prompting its completion.

The Death CRF is provided immediately after the occurrence or outcome of death is reported. Initial and follow-up reports regarding death must be completed within one week of when the death is reported.

In addition, all deaths will require a specific death data collection tool to be completed. The death data collection tool includes questions regarding cardiovascular (including sudden cardiac death) and noncardiovascular death.

8.3.10. Toxicity Management

Adverse events that occur during the trial should be evaluated by the Investigator and graded according to the Division of AIDS (DAIDS) toxicity scales (See Section 10.4. “Division of AIDS Table for Grading the Severity of Adult and Pediatric Adverse Events”). Additional information regarding detecting, documenting and reporting AEs and SAEs are available in Section 8.3 and Section 10.2.

8.3.10.1. Treatment Interruption Due to an Adverse Event

IP may be interrupted at the discretion of the investigator and according to the severity of the AE. If one or more ART medication is held due to toxicity or AEs, all ART medications should be held to reduce the risk of development of resistance taking into account the length of the planned interruptions and the PK half-life of each ART of the regimen, in order to minimize the risk of development of resistance.

No toxicity-related dose reductions of IP will be allowed. IP should be restarted as soon as medically appropriate; in general, for oral dosing, this should be no longer than 14 days after discontinuation (unless Grade 3 or 4 toxicities persist). Any interruption in therapy during the Maintenance Phase, oral dosing, of greater than 7 consecutive days must be discussed with and agreed by the Medical Monitor prior to resumption of therapy. The Medical Monitor must be contacted upon becoming aware of resumption in therapy, if therapy was resumed without prior approval (Section 6.9). **IM dosing is expected to occur during the week in which the participant's projected visit falls (as according to the first injection visit). An additional (+ or -) 7-day window, from the projected visit date, is allowable for IM dosing but not preferred.** Any interruption outside of this guidance **MUST** be discussed with the Medical Monitor prior to reinitiating IM IP (see Section 6.9.1).

Guidance is provided below on general participant management and IP interruptions based on the severity of the AE. Information regarding permitted substitutions \ is provided in Section 6.8. All changes in the IP regimen must be accurately recorded in the participant's eCRF.

Note: For participants receiving an ABC-containing product as part of the background regimen during the Long-Term Follow-Up (LTFU) Phase, in the event of a discontinuation of ABC for any reason, re-initiation of this drug should be undertaken with caution. The investigator should obtain a complete history of the events surrounding the discontinuation of the ABC-containing product, evaluate for the possibility of a clinically suspected HSR, and initiate participant management as outlined in the Local Country Prescribing Information, regardless of a participant's *HLA-B*5701* status. Screening for the presence of *HLA-B*5701* is recommended prior to reinitiating treatment with ABC-containing products in participants of unknown *HLA-B*5701* status who have previously tolerated ABC but is not required to confirm study eligibility.

8.3.10.2. Grade 1 or Grade 2 Toxicity/Adverse Event

Participants who develop a Grade 1 or Grade 2 AE or toxicity may continue study drug at the discretion of the investigator. Participants who choose to withdraw from the study due to a Grade 1 or 2 AE should have study withdrawal and follow-up evaluations completed.

Participants who develop ALT \geq 3 times ULN while on study must consult with Medical Monitor prior to initiation or continuation of CAB LA + RPV LA

8.3.10.3. Grade 3 Toxicity/Adverse Event

Participants who develop a Grade 3 AE or toxicity should be managed as follows:

- If the Investigator has compelling evidence that the Grade 3 AE or toxicity has not been caused by IP, dosing may continue after discussion with the Medical Monitor.
- Participants who develop a Grade 3 AE or toxicity, which the Investigator considers related or possibly related to the IP, should have the IP withheld and be rechecked each week until the AE returns to Grade 2. Once the AE is Grade ≤ 2 , IP may be re-started.
- Should the same Grade 3 AE recur within 28 days in the same participant, the IP should be permanently discontinued and the participant withdrawn from study.
- Participants experiencing Grade 3 AEs requiring permanent discontinuation of IP should be followed weekly until resolution of the AE and to have withdrawal study evaluations completed. A follow-up visit should be performed 4 weeks after the last dose of IP. Any participant receiving at least one dose of CAB LA and /or RPV LA who discontinue IP / Withdraw will initiate treatment with HAART and enter the LTFU Phase for 52 weeks of follow up.
- Participants with Grade 3 asymptomatic laboratory abnormalities should be investigated for all potential non-drug related causes, and, following discussion with the Medical Monitor, may continue IP if the Investigator has compelling evidence that the toxicity is not related to IP, with the exception of liver chemistry stopping criteria (See Section 8.3.11.1). Isolated Grade 3 lipid abnormalities do not require withdrawal of IP.

8.3.10.4. Grade 4 Toxicity/Adverse Event

- Participants who develop a Grade 4 AE or toxicity must have IP permanently discontinued. However, if the Investigator has compelling evidence that the AE is not causally related to the IP, dosing may continue after discussion with, and assent from, the Medical Monitor. Participants should be rechecked each week until the AE returns to Grade 2.
- Participants experiencing Grade 4 AEs requiring permanent discontinuation of IP should be followed weekly until resolution of the AE and encouraged to complete the withdrawal and follow-up study evaluations as noted above. Any participant receiving at least one dose of CAB LA and /or RPV LA who discontinue IP / Withdraw will initiate treatment with HAART and enter the LTFU Phase for 52 weeks of follow up.
- Participants with Grade 4 asymptomatic laboratory abnormalities should be investigated for all potential non-drug related causes, and, following discussion with the Medical Monitor, may continue therapy if the Investigator has compelling evidence that the toxicity is not related to IP, with the exception of liver chemistry stopping criteria (See Section 8.3.11.1). An in-clinic follow-up visit will be performed approximately 4 weeks after the last dose of study medication if AEs, SAEs, or laboratory abnormalities considered potentially harmful to the participant are ongoing at the last on-study visit. Isolated Grade 4 lipid abnormalities do not require withdrawal of IP.

8.3.11. Specific Toxicities/Adverse Event Management

General guidelines for the management of specific toxicities that are considered to be associated with treatment of HIV patients.

Participants who permanently discontinue study drug for reasons of toxicity should be followed weekly until resolution of the AE and encouraged to complete the withdrawal and Follow-up study evaluations as noted in Section 8.3.3.

8.3.11.1. Liver Chemistry Stopping and Follow-up Criteria

Liver chemistry threshold stopping criteria have been designed to assure participant safety and to evaluate liver event etiology during administration of study drug and the follow-up phase.

8.3.11.2. Seizures

A small number of seizure cases have been reported following CAB administration (less than 1% of all those receiving CAB in clinical studies).

ViiV Healthcare has reviewed these cases in detail and does not believe they constitute a reasonable likelihood of causation associated with CAB. This assessment is supported by the lack of preclinical signal, class effect or known CNS mechanism, the relatively low frequency of seizures relative to expected rates in both healthy and HIV positive participants and clinical confounders in each case. The Sponsor considers the risk of developing seizures on the study as being no higher than that of the rest of the HIV-1 infected population.

Seizures that occur on study should be managed according to the local guidelines on emergency seizure management which may include treatment with benzodiazepines, general supportive treatment, exclusion of metabolic and toxicological abnormalities using laboratory tests, septic workup and excluding underlying structural abnormalities with neuroimaging.

Where seizures occur, the Sponsor would like to better characterize these occurrences to enable systematic analyses.

Investigators are requested to document and report seizure or possible seizure events promptly (within 24 hours of learning of the event) to the Sponsor for evaluation and onward reporting. Data should be documented on the appropriate eCRF seizure page.

8.3.11.3. Decline in Renal Function

Participants who experience an increase in serum creatinine from Baseline of 45 micromoles/liter ($\mu\text{Mol/L}$) (or 0.5 milligrams/deciliter [mg/dL]) should return for a confirmatory assessment within 2 to 4 weeks. A urinalysis and urine albumin/creatinine and urine total protein/albumin ratios should also be done at this confirmatory visit. If the creatinine increase is confirmed, the investigator should contact the study medical monitor to discuss additional follow-up and medical management.

Participants who have a decline in the estimated GFR (using the CKD-EPI method) of >50% from Baseline must return for a confirmatory assessment as soon as possible [Levey, 2009]. A urinalysis and urine albumin/creatinine and urine protein/creatinine ratios should also be done at this confirmatory visit. If the estimated GFR has declined by >50% (confirmed), then study drug should be withheld, and the investigator should contact the study medical monitor to discuss the rationale for restarting study drugs (if appropriate). Consideration for confounding factors (e.g., background therapy, other medications, dehydration, concurrent conditions) should be taken into account, and a nephrology consult may be obtained.

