Participants must be discontinued from study treatment for any of the following reasons:

- Participants who are not eligible to continue into the Maintenance Phase.
- Participants who are not eligible, or do not wish to continue on to the Extension Phase.
- Virologic withdrawal criteria as specified in Section 7.1.6 are met;
- Participant requires substitution of ART;
- Participant requires substitution or dose reduction of CAB LA or RPV LA (oral bridging supply and potential for a second loading dose may be permissible following discussion with the Medical Monitor).
- Liver toxicity where stopping criteria are met and no compelling alternate cause is identified (see Section 7.1.2);
- Renal toxicity is met and no compelling alternate cause is identified;
- QT interval (QTc) interval >550 msec from three or more tracings separated by at least 5 minutes and considered causally related to IP.
- Grade 4 clinical AE considered causally related to study drug;
- Participant has a Grade 3 or higher rash or Grade 2 rash with evidence of systemic involvement and no compelling alternative cause is identified
- Pregnancy (intrauterine), regardless of termination status of pregnancy (for participants on BIK only) Participant withdrew consent

Efficacy data for participants withdrawing from the study will be considered evaluable up to the point at which they are withdrawn using the same criteria for evaluability as for participants who complete the study.

Safety data for all participants who receive any amount of study drug, including participants who withdraw from the study, will be included in evaluations of safety.

All data from the Withdrawal visit will be recorded, as they comprise an essential evaluation that should be done prior to discharging any participant from the study.

The following actions must be taken in relation to a participant who fails to attend the clinic for a required study visit:

- a. The site must attempt to contact the participant and re-schedule the missed visit as soon as possible.
- b. The site must counsel the participant on the importance of maintaining the assigned visit schedule and ascertain whether or not the participant wishes to and/or should continue in the study.
- c. In cases where the participant is deemed 'lost to follow up', the investigator or designee must make every effort to regain contact with the participant (where possible, 3 telephone calls and if necessary, a certified letter to the participant's

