8.2.2. Laboratory Assessments

All protocol required laboratory assessments, as defined in the SoA (see Section 1.3), must be performed by the central laboratory. Laboratory assessments must be conducted in accordance with the Central Laboratory Manual and Protocol SoA. Laboratory requisition forms must be completed, and samples must be clearly labeled with the participant number, protocol number, site/center number, and visit date. Details for the preparation and shipment of samples will be provided by the central laboratory. Reference ranges for all safety parameters will be provided to the site by the central laboratory.

- The investigator must review the laboratory report, document this review, and record any clinically relevant changes occurring during the study in the AE Section of the CRF. The laboratory reports must be filed with the source documents. Clinically significant abnormal laboratory findings are those which are not associated with the underlying disease, unless judged by the investigator to be more severe than expected for the participant's condition.
- All laboratory tests with values considered clinically significantly abnormal during participation in the study should be repeated until the values return to normal or baseline or are no longer considered significantly abnormal by the investigator or medical monitor.
- If such values do not return to normal/baseline within a period of time judged reasonable by the investigator, the etiology should be identified and the sponsor notified.
- All protocol-required laboratory assessments must be conducted in accordance with the laboratory manual and the protocol Time and Events table.

If additional non-protocol specified laboratory assessments are performed at the institution's local laboratory and result in a change in participant management or are considered clinically significant by the investigator (e.g., SAE or AE or dose modification) the results must be recorded in the eCRF. Local laboratory services may be used to verify pending laboratory parameters only after consultation and agreement with the study team.

Refer to the lab manual for appropriate processing and handling of samples to avoid duplicate and/or additional blood draws.

Labs will be automatically graded by the central lab according to the DAIDS toxicity scales (See Section 10.4 "Division of AIDS Table for Grading the Severity of Adult and Pediatric Adverse Events").

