Calcium, High (mg/dL; mmol/L) ≥ 7 days of age	10.6 to < 11.5 2.65 to < 2.88	11.5 to < 12.5 2.88 to < 3.13	12.5 to < 13.5 3.13 to < 3.38	≥ 13.5 ≥ 3.38
< 7 days of age	11.5 to < 12.4 2.88 to < 3.10	12.4 to < 12.9 3.10 to < 3.23	12.9 to < 13.5 3.23 to < 3.38	≥ 13.5 ≥ 3.38
Calcium (Ionized), High (mg/dL; mmol/L)	> ULN to < 6.0 > ULN to < 1.5	6.0 to < 6.4 1.5 to < 1.6	6.4 to < 7.2 1.6 to < 1.8	≥ 7.2 ≥ 1.8
Calcium, Low (mg/dL; mmol/L) ≥ 7 days of age	7.8 to < 8.4 1.95 to < 2.10	7.0 to < 7.8 1.75 to < 1.95	6.1 to < 7.0 1.53 to < 1.75	< 6.1 < 1.53
< 7 days of age	6.5 to < 7.5 1.63 to < 1.88	6.0 to < 6.5 1.50 to < 1.63	5.50 to < 6.0 1.38 to < 1.50	< 5.50 < 1.38
Calcium (Ionized), Low (mg/dL; mmol/L)	< LLN to 4.0 < LLN to 1.0	3.6 to < 4.0 0.9 to < 1.0	3.2 to < 3.6 0.8 to < 0.9	< 3.2 < 0.8
Cardiac Troponin I, High	NA	NA	NA	Levels consistent with myocardial infarction or unstable angina as defined by the local laboratory
Creatine Kinase, High	3 to < 6 x ULN	6 to < 10x ULN	10 to < 20 x ULN	≥ 20 x ULN
Creatinine, High *Report only one	1.1 to 1.3 x ULN	> 1.3 to 1.8 x ULN OR Increase to 1.3 to < 1.5 x participant's baseline	> 1.8 to < 3.5 x ULN OR Increase to 1.5 to < 2.0 x participant's baseline	≥ 3.5 x ULN OR Increase of ≥ 2.0 x participant's baseline
Creatinine Clearance¹⁴ or eGFR, Low *Report only one	NA	< 90 to 60 ml/min or ml/min/1.73 m ² OR 10 to < 30% decrease from participant's baseline	< 60 to 30 ml/min or ml/min/1.73 m ² OR 30 to < 50% decrease from participant's baseline	< 30 ml/min or ml/min/1.73 m ² OR ≥ 50% decrease from participant's baseline or dialysis needed
Glucose (mg/dL; mmol/L) Fasting, High	110 to 125 6.11 to < 6.95	> 125 to 250 6.95 to < 13.89	> 250 to 500 13.89 to < 27.75	≥ 500 ≥ 27.75
Nonfasting, High	116 to 160 6.44 to < 8.89	> 160 to 250 8.89 to < 13.89	> 250 to 500 13.89 to < 27.75	≥ 500 ≥ 27.75

¹⁴ Use the applicable formula (i.e., Cockcroft-Gault in mL/min or Schwartz, MDRD, CKD-Epi in mL/min/1.73m²). Sites should choose the method defined in their study and when not specified, use the method most relevant to the study population.

*Reminder: Choose the method that selects for the higher grade.

Chemistries

PARAMETER	GRADE 1 MILD	GRADE 2 MODERATE	GRADE 3 SEVERE	GRADE 4 POTENTIALLY LIFE- THREATENING
Glucose, Low (mg/dL; mmol/L) ≥ 1 month of age	55 to 64 3.05 to <3.55	40 to <55 2.22 to <3.05	30 to <40 1.67 to <2.22	<30 <1.67
< 1 month of age	50 to 54 2.78 to <3.00	40 to <50 2.22 to <2.78	30 to <40 1.67 to <2.22	<30 <1.67

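### For a confirmed eGFR fall of more than 50% with no compelling non-drug cause, Protocol 7.1, 8.3.10.4 and 8.3.11.3 give different stopping rules and no order of precedence

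*Protocol*

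**What the plan says.** Four parts of the Protocol bear on the same laboratory event.

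- **Appendix 4 (DAIDS grading table).** For low creatinine clearance or eGFR, one of the Grade 4 criteria is "≥ 50% decrease from participant's baseline or dialysis needed". Section 8.2.2 puts this scale to work: "Labs will be automatically graded by the central lab according to the DAIDS toxicity scales".
- **Section 8.3.10.4 (Grade 4).** The default is "Participants who develop a Grade 4 AE or toxicity must have IP permanently discontinued". The same bullet qualifies it: "if the Investigator has compelling evidence that the AE is not causally related to the IP, dosing may continue", after discussion with the Medical Monitor and with the monitor's assent. A later bullet says that participants with asymptomatic Grade 4 laboratory abnormalities "may continue therapy if the Investigator has compelling evidence that the toxicity is not related to IP", except where liver stopping criteria apply.
- **Section 8.3.11.3 (decline in renal function).** A fall in eGFR of more than 50% calls for a confirmatory assessment. When the repeat result bears the fall out, the instruction is "then study drug should be withheld, and the investigator should contact the study medical monitor to discuss the rationale for restarting study drugs". Restart is envisaged only where suitable, and confounding factors are to be considered.
- **Section 7.1 (mandatory discontinuation list).** One item reads "Renal toxicity is met and no compelling alternate cause is identified". It gives no threshold and refers to no other section. The liver item just above it refers to 7.1.2, and the QTc item just below it states its own limit.

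**The concern.** A stopping rule should give one answer for one event. Here an investigator with a confirmed eGFR fall above 50% finds a permanent stop in one section, a hold with possible restart in another, and in a third a mandatory stop tied to a term that is not defined.

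The difference matters to the participant. After even one injection, permanent discontinuation means moving to other antiretroviral therapy and 52 weeks of long-term follow-up (4.1.4 and 8.3.10.4). A temporary hold followed by restart does not. What is at stake is participant safety and consistent conduct of the trial.

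**Working it through.** The plan gives no figure to reproduce. The check compares thresholds and then the action each section gives.

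**Step 1: thresholds.** Section 8.3.11.3 acts on a fall above 50%. Appendix 4 assigns Grade 4 to a fall of 50% or more. Every value above 50% is also at least 50%, so every event that meets 8.3.11.3 is Grade 4 and falls under 8.3.10.4 as well.

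**Step 2: actions for a confirmed fall above 50%.**

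| Section | No compelling non-drug cause | Compelling non-drug cause |
|---|---|---|
| 8.3.10.4 | Permanent discontinuation | Dosing may continue, with the monitor's assent |
| 8.3.11.3 | Withhold; discuss restart with the monitor | Withhold; discuss restart with the monitor |
| 7.1 | Must discontinue, if the event counts as renal toxicity | Not triggered |

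In the first column the sections conflict: a stop without return against a hold with possible return. In the second column all three leave a way to continue or resume. The remaining difference is that 8.3.11.3 withholds drug first, while 8.3.10.4 lets dosing go on.

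**Step 3: triggers.** Section 8.3.11.3 needs a confirmed fall above 50%. Section 8.3.10.4 applies to any Grade 4 toxicity, so from 50%, and states no confirmation step. A first, unconfirmed result can therefore trigger 8.3.10.4 before 8.3.11.3 calls for any hold.

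**Step 4: what 7.1 refers to.** Its renal item could mean the creatinine rule or the eGFR rule in 8.3.11.3, the tubular dysfunction rule in 8.3.11.3.1, or the proteinuria rule in 8.3.11.4. Nothing in 7.1 says which. The separate Grade 4 item in 7.1 covers clinical adverse events considered causally related, so it does not settle a laboratory finding.

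**Step 5: precedence.** Sections 8.3.10.3 and 8.3.10.4 name liver chemistry and isolated lipid abnormalities as special cases; renal function is not named. Section 8.3.11 introduces itself as general guidance and claims no priority over 8.3.10.

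**The case against.** The strongest reply is that the sections can be read together: withhold, investigate, and restart only if another cause is found. On that reading 8.3.11.3 is simply the way in which the non-relatedness exception of 8.3.10.4 and the causality proviso of 7.1 are applied. This stands in part. Neither 8.3.10.4 nor 7.1 is unconditional, and where a compelling other cause exists the outcomes largely converge. It fails in the remaining case, because 8.3.11.3 does not make restart depend on finding another cause. Treating the specific section as overriding the general one is also something the reader must supply; the Protocol does not say it.

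Three stronger readings are tempting, and the document does not support them.

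- **Stopping will vary freely from site to site.** Section 6.9 requires decisions on interruption and resumption to be discussed with the medical monitor in advance, and 8.3.10.4 and 8.3.11.3 also bring the monitor in. That limits variation between sites, although the monitor still has no single rule to apply.
- **The creatinine and QTc rules conflict in the same way.** A creatinine recheck in 2 to 4 weeks can go alongside a Grade 3 hold. A temporary hold for a related QTc of 501 to 550 msec is compatible with withdrawal above 550 msec. These rules overlap but do not contradict each other.
- **The comparison of discontinuations due to adverse events is distorted between arms.** The only renal rate given is serious renal events in under 1% of BIK participants through Week 48 (2.3.1). Applied to the 218 BIK participants in Table 7, that is fewer than 0.01 × 218 = 2.18, or about two. Serious events are only a proxy for confirmed eGFR falls above 50%, but the figure gives no ground for claiming a material effect on this endpoint.

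**Conclusion.** The contradiction is real but narrow. For a confirmed eGFR fall above 50% with no compelling non-drug cause, 8.3.10.4 requires a permanent stop, 8.3.11.3 allows restart to be discussed, and 7.1 relies on an undefined term. Two lesser mismatches remain: whether drug is held while a non-drug cause is being established, and whether the fall must be confirmed before action.

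The overlap in rules is total, since every 8.3.11.3 eGFR event is Grade 4. The number of participants affected cannot be derived from the Protocol and is probably small. The conclusion rests on the DAIDS grade governing action under 8.3.10.4, as that section and 8.2.2 indicate, and on no precedence being stated elsewhere in the Protocol. The point concerns participant safety and consistent conduct; no effect on the primary result is claimed.

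**What to change.** Reconcile 7.1, 8.3.10.4 and 8.3.11.3. State in 8.3.10.4 which section governs a decline in renal function, as is already done there for liver chemistry and lipids. In 7.1, replace the bare renal item with a cross-reference to that section, matching the liver item. The reconciled text should also say whether the fall must be confirmed before action, whether the threshold is above 50% or 50% and over, whether drug is held during assessment, and whether restart depends on causality. Which rule applies is for the sponsor to decide.

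The cost is a wording amendment, with no new assessments or data collection and no change to sample size or analysis.
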